The variables on decision making with respect to risk, time and social considerations will be obtained from a short version of the Global Preferences Survey (<https://www.briq-institute.org/global-preferences/home>), a questionnaire on economic preferences (Falk 2016, 2018) . In particular, the blocks administered will include those relating to preferences against risk, time (patience) and social values.

In addition, there will be a citizen science component in which students will propose a set of factors that they believe can influence attention. Specifically, each class will design a 10-item questionnaire with such factors at the beginning of the study. The final questionnaire that will be administered to students during the experiment will be composed of 25 questions selected from the pool of proposed questions. At the end of the study, the items in this questionnaire will be compared with the results of the attention test as a way to validate the students' hypotheses.

Outcome Measures

The following variables will be considered as primary outcome measures:

1. Response speed consistency throughout the Attention Network Task-Flanker Task (post ANT). Calculated as hit reaction time standard error for correct responses (HRT-SE). A higher HRT-SE indicates highly variable reactions related to inattentiveness
2. Combined risk taking score. Risk taking = $0.4729985 \times \text{"Risk preference score"} + 0.5270015 \times \text{"Willingness to take risks"}$, that follows the parameters of Falk et al (2018), where the "Risk preference score" is the final node in the risk tree (see the online appendix of Falk et al (2018)), which is a value between 1 and 32, ranked by the level of risk aversion, and the "Willingness to take risks" refers to the answer to the question on one's willingness to take risks.
3. Combined patience score. Patience = $0.7115185 \times \text{"Time preference score"} + 0.2884815 \times \text{"Self assessment of patience"}$, that follows the parameters of Falk et al (2018), where the "Time preference score" is the final node in the time tree (see the online appendix of Falk et al (2018)), which is a value between 1 and 32, ranked by the level of patience, and the "Self assessment of patience" refers to the answer to the question on the self-assessment of patience (willingness to give up something today).

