Analysis on Decision-making with respect to Risk, Time and Social Considerations

Outcomes

The primary outcomes of analysis will be the (1) risk taking scores, (2) time preference scores, (3) the positive reciprocity scores, (4) the altruism scores, and (5) the self-assessment of trust. All the scores will be measured from the responses to the questionnaire, which is a subset of the questionnaire in Spanish used in Falk et al (2018). For each of the traits (risk preferences, time preferences, positive reciprocity, altruism, and trust), an individual-level index will be computed that aggregates responses across different survey items following the methodology in Falk et al. (2018).

Analysis Methods

The analysis will follow the basic analysis of Falk et al (2018), where groups, instead of being countries, will be our arms. In addition, we will follow the empirical strategy described above for the analysis on attention. That is, we will perform regression analysis, controlling for the relevant observable variables such as gender, age, cognitive ability, attention outcomes, and other physical variables measured at the time of the experiments such as temperature, relative humidity, or average CO₂ concentrations. We will also control for outliers, and will study heterogeneous treatment effects.

Missing Data

In terms of missing values in the questionnaire on preferences, we will follow the methodology of Falk et al (2018, Section I.H): “If one (or more) survey items for a given preference were missing, then the missing items will be predicted using the responses to the available items:

- Suppose the preference was measured using two items, call them *a* and *b*. For those observations with missing information on *a*, the procedure will be to predict its value based on the answer to *b* and its relationship to *a*, which was estimated by regressing *b* on *a* for the subsample of subjects who had nonmissing information on both, *a* and *b* (on the world sample).
- For the unfolding-brackets time and risk items, the imputation procedure will be similar, but making additional use of the informational content of the responses of participants who started but did not finish the sequence of the five questions. Again suppose that the preference is measured using two items and suppose that *a* (the staircase measure) is missing. If the respondent did not even start the staircase procedure, then imputation will be done

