using the methodology described above. On the other hand, if the respondent answered between one and four of the staircase questions, a will be predicted using a different procedure. Suppose the respondent answered four items such that his final staircase outcome would have to be either x or y. A probit was run of the “x vs. y” decision on b, and the corresponding coefficients were used to predict the decision for all missing values (note that this constitutes a predicted probability). The expected staircase outcome will be then obtained by applying the predicted probabilities to the respective staircase endpoints, i.e., in this case x and y. If the respondent answered three (or less) questions, the same procedure was applied, the only difference being that in this case the obtained predicted probabilities were applied to the expected values of the staircase outcome conditional on reaching the respective node. Put differently, the procedure outlined above was applied recursively by working backwards through the “tree” logic of the staircase procedure, resulting in an expected value for the outcome node.

– If all survey items for a given preference were missing, then no imputation will take place”

Statistical Software

Analyses will be conducted in Stata and Matlab.

References

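### The SAP predicts a missing preference item from its partner using a regression in the wrong direction, on a sample it does not define

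*SAP*

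**What the plan says.** The rule is in the SAP, Analysis on Decision-making, under Missing Data. It opens "In terms of missing values in the questionnaire on preferences, we will follow the methodology of" the cited global preferences study and then reproduces that study's procedure in quotation marks, partly changed to the future tense. Four cases are distinguished:

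- **One of two items missing.** Item *a* is predicted from the answer to *b* and from the relationship between them, "which was estimated by regressing *b* on *a* for the subsample of subjects who had nonmissing information on both" ("on the world sample").
- **Staircase never started.** "If the respondent did not even start the staircase procedure, then imputation will be done" by the same two-item rule.
- **Staircase partly answered.** A probit is run of the remaining "decision on b, and the corresponding coefficients were used to predict the decision for all missing values". The predicted probabilities are then applied to the possible endpoints.
- **Nothing answered.** "If all survey items for a given preference were missing, then no imputation will take place".

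The Protocol, Outcome Measures, builds each of the four scores as a weighted sum of two items. The risk staircase item is "which is a value between 1 and 32, ranked by the level of risk aversion", and the patience staircase has the same range. Trust is a single question. All five are listed as primary outcomes.

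**The concern.** In a regression of *b* on *a*, *b* is the outcome and *a* the predictor. The task here is the reverse: *b* is known and *a* is wanted. A programmer who follows the sentence has two literal choices. One is to solve the fitted line for *a*. The other is to put *b* into an equation that returns values of *b*. Neither gives a sound prediction of *a* on raw items.

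The SAP also becomes inconsistent within a single item. A student who answered one to four staircase questions is imputed by regressing the missing decision on *b*, with a result that stays within the scale. A student who answered none is imputed by the reversed regression, with no bound.

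The preference survey is the last activity of the two-hour session, so some unstarted items are plausible. The imputed values go straight into primary composites.

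The sample is a separate problem. The words "on the world sample" have no defined meaning in a trial of 14-15-year-olds in the Barcelona area. They have no part in the direction error.

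**Working it through.** The documents give no figure to reproduce: no item correlation, item SD or missing rate. Everything below rests on stated assumptions.

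**Inputs from the documents.** Weights (Protocol, Outcome Measures): risk staircase 0.4729985 and partner 0.5270015; patience staircase 0.7115185 and partner 0.2884815; gift 0.5152962 and partner 0.4847038; donation 0.3649952 and partner 0.6350048. Staircase range: 1 to 32.

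**Assumptions.** Correlation r between the two items of 0.2 to 0.5; items missing completely at random; staircase mean 16.5 and SD 9.23 (even spread over 1 to 32); for the raw-scale example, a 0-10 partner item with mean 5 and SD 2.5.

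**1. Slopes.**
- *a* on *b*: slope r·SD(a)/SD(b), so imputed SD = r·SD(a).
- *b* on *a*, inverted: slope SD(a)/(r·SD(b)), so imputed SD = SD(a)/r.
- Ratio of the two: 1/r². This is 25, 11 and 4 at r = 0.2, 0.3 and 0.5. The inverted imputed SD is 5.0, 3.3 and 2.0 times SD(a).

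**2. Inverted line on the staircase.** At r = 0.3, *b* at ±2 SD gives 16.5 ± 2 × 9.23/0.3, about -45 to 78. The *a*-on-*b* line gives 16.5 ± 2 × 0.3 × 9.23, about 11 to 22. The share of imputed values outside 1 to 32 is 2 × [1 − Φ(15.5·r/9.23)], with *b* taken as normal: 74%, 61% and 40% at r = 0.2, 0.3 and 0.5.

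**3. Line used without inversion, raw items.** Slope = 0.3 × 2.5/9.23 = 0.081; intercept = 5 − 0.081 × 16.5 = 3.66. A student with the average *b* of 5 is imputed 3.66 + 0.081 × 5, about 4, against a staircase mean of 16.5. If both items are standardised first, this slope equals r and the problem disappears.

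**4. Composite variance under inversion (standardised items).** Let w₁ be the weight of the missing item and w₂ that of its partner. Complete rows: V = w₁² + w₂² + 2w₁w₂r. Imputed rows: V* = (w₁/r + w₂)². With a proportion p imputed, the variance rises by p(V*/V − 1).

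Risk at r = 0.3: V = 0.651 and V* = (1.577 + 0.527)² = 4.425, so V*/V = 6.80 and the rise is 5.80p.

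| Score (item missing) | r = 0.3, p = 2% | r = 0.3, p = 5% | r = 0.3, p = 10% | r = 0.5, p = 1% |
|---|---|---|---|---|
| Risk (staircase) | 12% | 29% | 58% | 1.9% |
| Patience (staircase) | 18% | 45% | 89% | 2.7% |
| Positive reciprocity (gift) | 13% | 32% | 65% | 2.1% |
| Altruism (donation) | 8% | 20% | 41% | 1.4% |

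**5. Power.** Hold the arm difference fixed and start from 80% power. At r = 0.3 and 5% missing, the composite SD rises by a factor of √1.290 = 1.136 for risk and √1.447 = 1.203 for patience. Power is Φ(2.80/1.136 − 1.96), about 69%, and Φ(2.80/1.203 − 1.96), about 64%. At 1% missing it is about 77% to 78%.

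**6. Conventional direction.** With V* = (w₁r + w₂)² and r = 0.3, the variance falls by about 3% (risk) and 6% (patience) at 10% missing. Imputed values between 11 and 22 stay within range.

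**The case against.** The best defence is that this is a transposed phrase. The stated aim is to predict *a* from *b*, the companion probit rule runs that way, and an analyst would probably fit *a* on *b* without hesitation. The text is quoted from a source that cannot be checked here, so the slip may not be the trial team's. This is a fair reading of the intention. It does not make the sentence correct, because the SAP adopts the quoted text as its own procedure.

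A reader might infer that the plan will produce wildly over-dispersed primary outcomes. The documents do not support that. It requires inversion, which the SAP never states, together with a low item correlation and a non-trivial missing rate.

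A reader might also infer that the SAP commits to coefficients from an external population. That is not established either. The past tense allows it, but the Analysis Methods section says the arms take the place of the source's countries. On that mapping the phrase could mean all trial students pooled.

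Nor do the documents show a biased arm comparison: the rule does not use arm. The SAP also plans to control for outliers and borrows the attention strategy, which includes DFBeta checks and re-analysis without influential subjects. These checks give some protection. However, they would handle an imputation artefact by removing students, which is a poor substitute for a correct rule.

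**Conclusion.** Wrong as written; minor to moderate severity. The direction of the regression is incorrect for its stated purpose and inconsistent with the SAP's rule for partly answered staircases. On raw items both literal uses fail, one through spread and the other through scale. Only an unstated step such as prior standardisation avoids both.

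The consequence is conditional. It ranges from negligible (r = 0.5 with 1% missing) to material (r = 0.3 with 5% or more missing, if the line is inverted). With similar missingness in the two arms, the cost is mainly precision.

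The scope is narrow: the four two-item scores, and only where one item is wholly missing and its partner was answered. Trust, partly answered staircases and wholly missing preferences are not affected. The undefined sample is a separate ambiguity about which data supply the coefficients and whether they apply to this age group.

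**What to change.** Replace the sentence in the SAP with:

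> *a* is predicted from *b* using the regression of *a* on *b*, estimated in trial students with both items observed, pooled over arms and without using arm.

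Delete the reference to a world sample. State whether items are standardised before fitting. Report the number of imputed values per item and arm. Add a sensitivity analysis restricted to students with both items observed. That analysis also shows how much the results depend on single imputation, which understates variance somewhat even in the right direction.

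The cost is one corrected sentence, one count table and one extra model run per score. No new data are needed.
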